2.3.2.4 Clinical toxicology of poly-ICLC

Poly-ICLC is the TLR3 agonist formulation most extensively tested in patients with infectious diseases and in subjects with a variety of different tumor types.

Prior to the availability of recombinant interferon, poly-ICLC was used clinically at high doses \geq 6mg/m² (about 170 μ g/kg) in patients with a variety of solid tumors and leukemia⁶¹. Fever, often above 40°C, was a common adverse event and the primary dose-limiting factor. Other common adverse events were flu-like symptoms (nausea, vomiting, arthralgia, myalgia and fatigue) and hypotension, thrombocytopenia and leukopenia. Once recombinant interferon became clinically available, the need to pursue high dose poly-ICLC was eliminated, and it became recognized that lower doses (10 – 50 μ g/kg) were highly effective at stimulating host defense and as an immune adjuvant.

By now, more than 400 patients with malignant gliomas have been entered on 7 clinical trials using low dose (1-2 mg total dose) poly-ICLC either as monotherapy or in conjunction with chemotherapy, radiation, or vaccine (Table 1). Furthermore, patients with various other solid tumors (prostate, colorectal, pancreatic, hepatocellular, breast, and ovarian cancers), in addition to patients with HIV/AIDS and multiple sclerosis have been treated on more than 10 additional clinical phase I and phase II studies. Overall, the drug has been well-tolerated across all studies and spectrum of diseases. The most common adverse events attributed as at least possibly related to poly-ICLC have included:

- bone marrow toxicity (leukopenia, neutropenia, thrombocytopenia, and anemia)
- reversible liver toxicity (AST/ALT elevations, LDH and alkaline phosphatase elevation)
- transient discomfort at the injection site
- transient fatigue/malaise
- transient flu-like symptoms

In a recently published phase I clinical trial, 11 patients with ovarian, fallopian tube, or primary peritoneal cancer were treated with poly-ICLC at a total dose of 1.4 mg in combination with Montanide-ISA-51 and synthetic over-lapping long peptides from NY-ESO-1. The vaccine was generally well-tolerated with grade 1-2 injection site reactions and fatigue as the only adverse

events that were considered possibly or definitely drug-related¹⁸. No grade 3 or 4 adverse events were reported. In another clinical study which recently completed accrual (ClinicalTrials.gov Identifier NCT01079741) 27 patients with high-risk melanoma received poly-ICLC at a total dose of 1.4 mg in addition to NY-ESO-1 protein ± Montanide-ISA-51 given s.q. every 3 weeks for 4 doses (in addition to 6 patients who received 0.35 mg and 0.70 mg, respectively of poly-ICLC on cohorts 1 and 2 of the dose escalation part of the trial). The vaccine was generally well-tolerated with grade 1 and 2 injection site reactions and transient, grade 1 or 2, flu-like symptoms that resolved after 12-48 hours ([REDACTED]).

Selected Clinical Trials with Low-Dose Poly-ICLC						
Protocol Title	Phase	Protocol Location	Indication	Status	N	Dosing Schedule
Long-term IM poly-ICLC in Malignant Glioma – a Pilot Study	I-II	Walter Reed	Malignant Glioma	Closed	67	IM 10-50 µg/kg 1-3 X week
Poly-ICLC in Recurrent Malignant Brain Tumors	I-II	MCV	Recurrent Glioma	Closed	99	IM 20 µg/kg 3 X week
Poly-ICLC in Malignant Pediatric Brain Tumors	I-II	L.A. Childrens Hosp	Pediatric Glioma	Closed	46	IM 20 µg/kg 2 X week
Poly-ICLC plus Radiation in Glioblastoma	II	NABTC 2001-05	Glioblastoma	Closed	31	IM 20 µg/kg 3 X week
Poly-ICLC in Recurrent Anaplastic Glioma	II	NABTC 2001-06	Recurrent Anaplastic Glioma	Closed	55	IM 20 µg/kg 3 X week
Poly-ICLC plus Temodar in Newly Diagnosed Glioblastoma	II	NABTT 2005-01	Glioblastoma	Closed	97	IM 20 µg/kg 3 X week
Pilot Study of MUC1 Vaccine plus poly-ICLC in Advanced Prostate Cancer	I-II	UPMC 05-086	Advanced Prostate Cancer	Closed	25	IM 25 µg/kg 2 X week
Poly-ICLC plus Dendritic Cell vaccine in Recurrent Gliomas	I-II	UPMC	Recurrent gliomas	Closed	25	IM 20 mcg/kg
Poly-ICLC plus HSP-HPVE7 Vaccine in Cervical Dysplasia	I	Nventa	Cervical Dysplasia	Closed	24	.05 – 2 mg
IntraTumoral (IT) poly-ICLC plus XRT and TACE in Liver Cancer	I-II	UMDNJ	Hepatoma, Metastatic liver cancers	Closed	24	1 mg IT + 1 mg IM 2xweek
A Randomized Controlled Phase I trial of Nasal Hiltonol	I	NIAID, NIH	Normal volunteers	Closed	50	0.25-4mg IN
CDX 1307 vaccine with poly-ICLC in metastatic cancers	I	Various	Metastatic Cancers	Closed	20	2 mg IM
Poly-ICLC with glioma associated peptide vaccine	I-II	UPMC	Grade II Gliomas	Closed	20	20 mcg/kg IM 2X Wk
MUC1 100-mer and poly-ICLC Vaccine for Colonic Polyposis	I/II	UPMC	Colonic Adenoma	Closed	45	.5 mg SC
Hiltonol + NYESO1 Protein Vaccine in Ovarian Cancer	I/II	MSKCC, LICR	Ovarian Cancer	Closed	10	1.4 mg SC
IntraTumoral PICLC and DC in Pancreatic CA	I/II	MUSC	Pancreatic Cancer	Closed	12	1 mg IT + IM

Selected Clinical Trials with Low-Dose Poly-ICLC						
Intratumoral PICLC and DC in Solid Cancers	I/II	Univ. Navarra Spain	Solid Cancers	Closed	15	1 mg IT
Pilot study of intratumoral and IM Poly-ICLC	I/II	Mt. Sinai MC, NY	Solid Cancers	Closed	8	1 mg IT+ IM
Poly-ICLC + CDX1401 + FLT3	I/II	CITN, Celldex	Melanoma	Closed	60	1 mg IT+ IM
IMA950 vaccine /Poly-ICLC, Keytruda	I/II	U. Geneva Suisse	Glioblastoma	Open	20	1 mg IM
MAGE A3 + Hiltonol in Myeloma	I/II	Univ. of Maryland	Myeloma	Closed	27	1 mg SC
DEC205 GAG Protein / Hiltonol	II	Rockefeller Univ.	HIV vaccine	Closed	40	1.5 mg SC
WT1 vaccine / Hiltonol / Basiliximab	I/II	U. Chicago	AM Leukemia	Closed	7	1 mg SC
In-Situ IT Autovaccination Hiltonol, FLT3, aPD1	I/II	Mt. Sinai MC, NY	Lymphoma	Open	40	1 mg
In Situ Autovaccination with IT Hiltonol,	II	Multicenter	Solid Tumors	Open	60	1 mg IT + IM
GAPVAC Trial, Europe	I	Multicenter	Glioblastoma	Closed	16	1 mg SC
A Personalized Cancer Neoantigen vaccine + Poly-ICLC, Nivolumab	I/II	Multicenter	Solid Cancers	Open	90	2 mg SC
In situ vaccination with durvalumab ± tremelimumab + IT Hiltonol	I/II	UVA, ISMMS	Solid Cancers	Open	36	1 mg IT
Pembrolizumab and poly-ICLC	I/II	Augusta U.	Colon Cancer	Open	45	1 mg IT
IM Poly-ICLC in Low grade Glioma	I/II	UCSD, Emory U	Pediatric Low Grade Glioma	Closed	23	20 mcg/kg IM
IM Hiltonol + aPD1/L1	II	Multicenter	Solid Cancers	Open	60	1 mg 2X wk

2.3.3 Montanide ISA-51 VG

Montanide ISA-51 VG (Seppic, Inc.) is a commercially available, mineral oil-based immune adjuvant analogous to incomplete Freund's adjuvant (IFA) that enhances the immune response to vaccination through various mechanisms. The depot effect of this water in oil emulsion results in slow release of the antigen from the injection site. The emulsion also protects the antigen from rapid degradation by enzymes, and can modify the electric charge of the antigen leading to enhanced immunogenicity⁶². In addition, the emulsion can create inflammation and stimulate the recruitment and possible activation of antigen presenting cells (APC) and even facilitate antigen uptake by APCs through interactions between the surfactant and cellular membranes. Lymphocyte trapping in draining lymph nodes is an additional mechanism of action of oil adjuvants contributing to prolonged cell-cell interactions in the lymph node. (Seppic Inc., data,

manufacturer of Montanide). Montanide ISA-51 VG must be mixed in a 1:1 ratio with aqueous vaccine preparation to form an emulsion for subcutaneous injection. The compound can be administered in repeat doses ranging from 0.5 ml to 2 ml.⁶²

Montanide has been tested in more than 200 clinical phase 1 – 3 cancer vaccine trials targeting melanoma and a number of other solid and hematologic malignancies. The compound has been generally well tolerated and induces transient local reactions such as tenderness, erythema, or edema at the injection site. Transient general reactions including fever, headache, and flu-like symptoms have also been observed. A clinical study of long peptides (~20-mer) derived from the HPV-16 E6 and E7 viral oncoproteins administered in Montanide showed clinical responses in women with vulvar intraepithelial neoplasia; tumor regressions were associated with the generation of HPV-specific, IFN- γ -producing CD4+ and CD8+ T cells^{15,16}.

Montanide-ISA-51 in combination with poly-ICLC and synthetic over-lapping long peptides from NY-ESO-1 has been administered to 11 patients with ovarian, fallopian tube, or primary peritoneal cancer in a phase I clinical trial. This vaccine was generally well-tolerated with grade 1-2 injection site reactions and fatigue as the only adverse events that were considered possibly or definitely drug-related¹⁸. No grade 3 or 4 adverse events were reported. In another clinical trial (ClinicalTrials.gov Identifier NCT01079741) 19 patients with high-risk melanoma received Montanide –ISA-51 combined with poly-ICLC and NY-ESO-1 protein given s.q. every 3 weeks for 4 doses. The vaccine was generally well-tolerated with grade 1 and 2 injection site reactions and transient, grade 1 or 2, flu-like symptoms that resolved after 12-48 hours⁶³.

2.3.4 Ipilimumab

Ipilimumab (BMS-734016, MDX010, MDX-CTLA4) is a fully humanized monoclonal immunoglobulin (Ig) G1 κ specific for human cytotoxic T lymphocyte antigen 4 (CTLA-4, CD152), which is expressed on a subset of activated T cells. CTLA-4 is a negative regulator of T cell activity. Ipilimumab is a monoclonal antibody that binds to CTLA-4 and blocks the interaction of CTLA-4 with its ligands, CD80/CD86. Blockade of CTLA-4 has been shown to augment T cell activation and proliferation, including the activation and proliferation of tumor infiltrating T-effector cells. Inhibition of CTLA-4 signaling can also reduce T-regulatory cell function, which may contribute to a general increase in T cell responsiveness, including the anti-tumor response.

Yervoy™ (Ipilimumab) has been approved for use in over 47 countries including the United States (US, Mar-2011), the European Union (EU, Jul-2011) and Australia (Jul-2011).

2.3.4.1 Preclinical Toxicology of Ipilimumab

Complete information on the pre-clinical toxicology studies can be found in the Ipilimumab Investigator Brochure (IB). The results of these toxicology studies are summarized in brief below.

Ipilimumab binds to human and cynomolgous monkey CTLA-4 with high affinity and blocks binding of CD80 (B7.1) and CD86 (B7.2) to CTLA-4. The proposed mechanism of action for Ipilimumab is interference of the interaction of CTLA-4 with its natural ligands, CD80/CD86, expressed on antigen presenting cells, which results in blockade of the inhibitory modulation for

T cell activation. CTLA-4 blockade by Ipilimumab resulted in augmentation of antibody responses to various T cell dependent antigens and suppression of tumor growth in mice.

The cynomolgous monkey was selected as the primary toxicology species because Ipilimumab binds specifically to macaque CTLA-4, but not to homologous CTLA-4 in other traditional toxicology species⁶⁴. Administration of Ipilimumab to cynomolgous monkeys resulted in marked enhancement of the immune response to a viral antigen (hepatitis B surface antigen), a cell-based vaccine (SK-mel) and to keyhole limpet hemocyanin.

In IV repeat-dose toxicology studies in monkeys, Ipilimumab was tolerated without adverse effects at doses up to 30 mg/kg/day administered every 3 days for 3 doses (peak serum concentrations \leq 682 μ g/mL)⁶⁵⁻⁶⁷ at 10 mg/kg (equivalent to human dose on a body-weight basis) administered weekly for 1 month⁶⁸ (mean area under the concentration-time curve 0-168h) and AUC (0-63days) of 31.6 mg·h/mL and 90.6 mg·h/mL respectively), at 1 mg/kg administered weekly for 10 weeks⁶⁹ and at doses up to 10 mg/kg/day administered approximately monthly for up to 6 months^{66,68,70,71}. In the pivotal 6-month toxicity study (10 mg/kg administered on days 0,28,56,84 and 140), treatment-related findings were limited to decreases in absolute and relative thyroid (44% to 50%) and testicular (27% to 50%) weights.

In an exploratory pharmacology study, severe colitis occurred after the second dose in 1 of 5 monkeys receiving Ipilimumab at 10 mg/kg approximately monthly in combination with 3 vaccines. The binding of Ipilimumab to CTLA-4 expressed on gut-associated lymphoid tissue was confirmed in human and monkey tissue-binding studies^{64,72,73} and suggests that these lymphocytes exist in an activated state, making them susceptible to CTLA-4 blockade. Two gastrointestinal toxicities (diarrhea and colitis) have emerged as significant immune related adverse events in the clinical studies with Ipilimumab (See 2.4.2.2 below).

The effects of Ipilimumab on reproduction and development were studied in an enhanced pre and postnatal development study in cynomolgous monkeys⁷⁴. Pregnant monkeys received Ipilimumab every 21 days from the onset of organogenesis through parturition at doses of 2.6 or 7.2 times the clinical exposure at a dose of 3 mg/kg or 0.9 to 2.1 times higher than the clinical exposure at a dose of 10 mg/kg every 21 days of Ipilimumab. Beginning in the third trimester, the Ipilimumab groups experienced increased maternal weight decrements; higher incidences of abortion, stillbirth, premature delivery and higher incidences of infant mortality in a dose-related manner. Infants exposed to 30 mg/kg/q3w had a lower mean body weight at birth that persisted for multiple months. Based on the results for the monkey reproductive system, Ipilimumab is not recommended for use during pregnancy unless the potential benefit justifies the potential risk to the fetus.

In summary, other than the events described above, Ipilimumab did not result in any adverse toxicities in any other monkeys in general toxicity studies when administered IV at doses up to 30 mg/kg for 1 week, 10 mg/kg weekly for 1 month, 1 mg/kg weekly for 10 weeks, or 10 mg/kg monthly for 6 months.

2.3.4.2 Clinical Toxicology of Ipilimumab

Except for pediatric patients, all the clinical studies reported in the Investigator Brochure utilized Ipilimumab delivered intravenously at doses of 3 mg/kg to 10 mg/kg, usually q3weeks X 4. As described in Section 6.1.3, the starting dose level utilized in this protocol results in approximately one thirtieth (1/30) the exposure compared to the 3 mg/kg i.v. dosing. Thus, the safety events observed with Ipilimumab delivered intravenously may be significantly greater than following limited local delivery, a hypothesis of this study.

Complete information on the clinical safety of Ipilimumab delivered intravenously at doses of 3 mg/kg and 10 mg/kg can be found in the Ipilimumab Investigator Brochure (IB) and are summarized in brief below.

Blockade of CTLA-4 by Ipilimumab leads to T cell activation with the potential for clinical inflammatory AEs primarily involving the skin (dermatitis, pruritis), GI tract (diarrhea/colitis), liver (hepatitis), endocrine glands (e.g., hypophysitis, adrenal and thyroid abnormalities) and other less frequent organs (e.g., uveitis/episcleritis). The majority of the inflammatory AEs are reversible with the guidance issued below. In rare cases, these inflammatory AEs may be fatal. Patients should be assessed for signs and symptoms of enterocolitis, dermatitis, neuropathy and endocrinopathy, and clinical chemistries (including liver function and thyroid function tests) should be evaluated at baseline and before each dose of Ipilimumab. GI (diarrhea and colitis) and skin (rash and pruritis)-related toxicities are the most common inflammatory events reported in studies with Ipilimumab. Suggested evaluation procedures for suspected GI, liver, skin, endocrine, neurological and ocular toxicities are described below. Early diagnosis and treatment intervention for inflammatory events can help prevent the occurrence of complications, such as GI perforation.

During evaluation of a suspected inflammatory AE, all efforts should be made to rule out neoplastic, infectious, metabolic, toxin or other etiologic causes. Serological, immunological, imaging, and biopsy with histology (e.g. biopsy-proven lymphocytic) data should be used to support the diagnosis of an immune-mediated toxicity or support an alternative cause of the AE.

In general, for severe inflammatory AEs, Ipilimumab should be permanently discontinued and systemic high-dose corticosteroid therapy should be initiated. For moderate immune-mediated AEs, Ipilimumab should be held or delayed and moderate dose corticosteroids should be considered. Upon improvement, corticosteroids should be tapered gradually over at least 1 month.

Based on limited current clinical experience, corticosteroids do not appear to adversely affect the antitumor response. For example, disease control was maintained in subjects with objective responses who received corticosteroid administration for concomitant serious inflammatory AEs.

The management guidelines for general inflammatory GI, liver, skin, endocrine, and neurological toxicities are provided in detail in Appendix 3 of the Investigators Brochure.

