5.2 Agent Administration

Agent	Treatment phase	Schedule**	Allowable Treatment Admin Window	Dose	Route
Nivolumab	Entire Duration	Every 4 weeks	± 3 days	480 mg flat dose	i.v.
Neoantigen Vaccine (peptides + poly-ICLC + Montanide® ISA-51 VG)*.***	Vaccination Phase	Week 12, 15, 18, and 21	± 3 days	
Poly-ICLC: 2 x 0.5 mg (0.25ml each)
 
Peptides: 2 x 300μg per peptide/0.75ml
 
Montanide® ISA-51 VG: 2 x 1ml
 
Total Neoantigen Vaccine Volume*: up to 2 x 1.6 ml
	Neoantigen Vaccine s.c. injections into up to 2 different anatomic sites
Ipilimumab	Vaccination Phase	Week 12, 15, 18, and 21	± 3 days	2 x 1.25 mg (0.25ml), 2.5 mg (0.5 ml) or 5 mg (1.0 ml) depending on the cohort	s.c injection within 1 cm of each Neoantigen Vaccine injection

*During NeoVax (personalized neoantigen peptides + Hiltonol) and Montanide mixing preparation there is a loss of 0.4 mL

**Please refer to section 5.2.1.2 regarding delays on vaccination therapy start

***If emulsion of either pool A or pool B or both pools A and B is unsuccessful after two attempts, the neoantigen vaccine will be prepared without Montanide as stated in section 8.6.3.

If one of the initial vaccine doses is not successfully emulsified with montanide after two attempts, the vaccine will be prepared without the Montanide (see table below and section 8.6.3).

During the vaccination treatment period if any of the two vaccine doses is not successfully emulsified with montanide after two attempts, the vaccine will be prepared without the Montanide.

Treatment plan if emulsion NeoVax – Montanide fails:

Agent	Treatment phase	Schedule**	Allowable Treatment Admin Window	Dose	Route
Nivolumab	Entire Duration	Every 4 weeks	\pm 3 days	480 mg flat dose	i.v.
NeoVax (peptides + poly-ICLC)***	Vaccination Phase	Week 12, 15, 18, and 21	\pm 3 days	
Poly-ICLC: 2 x 0.5 mg (0.25ml each)
 
Peptides: 2 x 300μg per peptide/0.75ml
 
Total NeoVax Volume: up to 1.0 ml (+/- 0.1 ml)
	NeoVax s.c. injections into up to 2 different anatomic sites
Ipilimumab	Vaccination Phase	Week 12, 15, 18, and 21	\pm 3 days	2 x 1.25 mg (0.25ml), 2.5 mg (0.5 ml) or 5 mg (1.0 ml) depending on the cohort	s.c injection within 1 cm of each NeoVax injection

***If emulsion of either pool A or pool B or both pools A and B is unsuccessful after two attempts the vaccine will be prepared without Montanide as stated in section 8.6.3

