5.2.1.2 Nivolumab plus neoantigen vaccine (NeoVax plus Montanide) / Ipilimumab Period

Patients will begin therapy with neoantigen vaccine (NeoVax plus Montanide) / Ipilimumab once the vaccine has been prepared and testing completed at week 12. Patients will receive Nivolumab at a flat dose of 480 mg as a 30 minutes (+/- 10 min.) i.v. infusion every 4 weeks (28 days). Nivolumab will be given 60 minutes (+/- 10 min) following local Ipilimumab administration.

If therapy with neoantigen vaccine (NeoVax plus Montanide) / Ipilimumab gets delayed, vaccination timepoints will be modified as follows:

Neoantigen vaccine (NeoVax plus Montanide) / Ipilimumab vaccination timepoints #2 (week 15), #3 (week 18), and #4 (week 21) will be moved accordingly so there is a window of three weeks (+/- 3 days) between each vaccination timepoint. If any of the vaccine administrations coincide with Nivolumab treatment, neoantigen vaccine (NeoVax plus Montanide) / local Ipilimumab will be administrated first and Nivolumab will be given 60 minutes (+/- 10 min) following local Ipilimumab administration.

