10. STUDY CALENDAR

Procedure ¹	Screen ²	Pre-Treatment ³	Pre-Vaccination Treatment				Vaccination Treatment								Post Vaccination		Follow Up ¹⁴
			0	4	8	10	12	13	15	16	18	19	20	21	22	24	Q4 weeks
Week	NA																
Informed Consent	X																
Med Hx	X																
Concomitant Medication	X	X	X	X	X	X	X	X	X	X	X	X	X	X	X	X	X
PE/Vitals/Pulse Ox	X		X	X	X	X	X	X	X	X	X	X	X	X	X	X	X
ECOG PS	X		X	X	X	X	X	X	X	X	X	X	X	X	X	X	X
Staging scans ³	X						X									X	X
CBC w/ diff	X		X	X	X	X	X	X	X	X	X	X	X	X	X	X	X
Serum Chem ⁴	X		X	X	X	X	X	X	X	X	X	X	X	X	X	X	X
12-lead EKG	X																
Pregnancy Testing ⁵	X		X	X		X	X		X		X						
Thyroid Stimulating Hormone ⁶	X																
Infectious Panel ⁷	X																
Urinalysis	X																
Blood draw for vaccine manufacturing ⁸	X																
HLA class I and II typing ⁹		X															
Nivolumab administration ¹⁰			X	X	X		X			X			X		X	X	X
Ipilimumab administration ¹¹																	
Neoantigen vaccine Administration ¹²																	
Tumor biopsy ^{11,*}		X ¹¹													X ¹¹		
Leukapheresis ^{12,*}		X ¹²													X ¹²		
Blood draw for immune response monitoring ^{13,*}			X ¹³		X ¹³										X	X	
Vaccine biopsy [*]																	
Adverse Events			X	X	X	X	X	X	X	X	X	X	X	X	X	X	X

*please see Vaccine + Ipilimumab administration and vaccine-related assessments table below

- 1 All study procedures should be performed within +/- 3 day window unless specified otherwise
- 2 Screening assessments must be completed within 30 days of, and prior to the first dose of Nivolumab on Week 0 Day 1. An additional 15 days is allowed for a repeat biopsy, if needed, to obtain adequate tissue for sequencing. This initial biopsy sample should have approximately 30% tumor cellularity and a minimum of 5-8 cores or 100 mm³ in order for sequencing to be completed

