- 3 +/- 14 day window for staging scans CT or MRI of other areas of disease (e.g. neck) should be obtained as clinically indicated. If IV contrast is contraindicated, a non-contrast CT and MRI may be used to evaluate sites of disease where a CT without contrast is not adequate. The imaging modality should remain consistent throughout the study and should be the same modality used at Screening. Photographs should be taken of one non-biopsied representative skin lesion, if feasible, on the same day that radiographic scans are obtained. The 100 day CT/MRI can be obtained within a +/-30-day window. If a patient has undergone a procedure (CT or MRI) that is within the allotted timeframe for evaluation, then the patient does not have to undergo an additional procedure. Clinical assessments must be based on RECIST v1.1. After the week 24 timepoint, staging scans should be performed every 12 weeks
- 4 Glucose, urea nitrogen, creatinine, sodium, potassium, calcium, total and direct bilirubin, AST, ALT, alkaline phosphatase
- 5 Women of childbearing potential (WOCBP) must have a negative serum or urine β -HCG pregnancy test. Urine or serum pregnancy test should be at screening, within 24 hours prior to receiving the first dose of study medication and then every 4 weeks while on treatment.
- 6 Thyroid stimulating hormone with reflex T4
- 7 HBsAg, HBcAb, HCV, HIV I/II Ab
- 8 At least two 10mL EDTA tubes will be collected for vaccine production purposes. The tubes will be kept frozen at the CRL until the day of shipment for DNA sequencing
- 9 Molecular HLA typing to be performed by Tissue Typing Laboratory (HLA-A, HLA-B, HLA-C, and HLA-DR)
- 10 Nivolumab treatment will start within 2 weeks of tumor biopsy and once histopathology report confirms melanoma and the biopsy sample is confirmed to have adequate tumor content for DNA sequencing. Nivolumab dosing every 4 weeks (+/- 3 days) until disease progression or intolerable toxicity (minimum 26 days between dosing). Nivolumab will be administered until intolerable toxicity, disease progression (unless treatment beyond progression is deemed to be beneficial for the patient) for a maximum duration of 24 months

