- 11 Tumor biopsies will be collected in patients with unresectable melanoma who have metastatic sites accessible to serial tumor biopsies within two weeks prior to Nivolumab treatment initiation. Tumor biopsy must contain $\geq 30\%$ of tumor cells. At a minimum, 5 core biopsies or a surgical tumor specimen of 100mm³ will be obtained. Skin punch biopsies of a skin lesion are also allowed. The collection of tumor biopsies for research purposes do not apply for patients with stage III melanoma
- 12 Leukapheresis procedure will be performed within 14 days before starting Nivolumab. At each Leukapheresis collection timepoint 2x10 mL EDTA tubes will be collected. These tubes should be dropped off at the IAL upon collection. If Leukapheresis cannot be performed a total of 200mL of blood should be drawn. If starting of vaccine administration gets delayed, week 20 leukapheresis will be collected before vaccination timepoint #4. A Leukapheresis during the Post-Vaccination treatment/ Followup period may be performed
- 13 Unless otherwise specified, 80 mL of blood will be drawn for immune monitoring.
- 14 Active Follow-Up: Participants removed from active study treatment will be followed at the following schedule until initiation of a new therapy for recurrent disease, withdrawal of consent, or death (whichever comes first):
 - At least every 3 months (+/- 2 weeks) for the first 2 years after initiation of study therapy,
 - At least every 4 months (+/- 2 weeks) for the third year after study therapy initiation,
 - At least every 6 months (+/- 4 weeks) thereafter, until 5 years have passed since study therapy initiationLong-Term Follow-Up: Participants removed from active follow-up for progression/initiation of a new therapy will enter long-term follow-up, where they will be followed via medical record review until death for survival. Updates to the CRFs are to be made approximately every six months
- * Please see table below

Neoantigen vaccine + Ipilimumab administration calendar and assessments related to vaccination timepoints

Procedure ¹	Pre-vaccine assessments	Neoantigen Vaccine Dose #1 ^c	Post vaccine dose 1 visit	Neoantigen Vaccine Dose #2 ^c	Post vaccine dose 2 visit	Neoantigen Vaccine Dose #3 ^c	Post vaccine dose 3 visit	Neoantigen Vaccine Dose #4 ^c	Post vaccine dose 4 visit
PE/vitals Concomitant Medications ECOG, CBC w/ diff, Serum Chemistry ²		X	X	X	X	X	X	X	X
Leukapheresis	X ^a							X ^a	
Tumor biopsy	X ^b							X ^b	

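### Thyroid tests recommended before each ipilimumab dose in Section 2.3.4.2 are not carried into the study calendars, which schedule TSH at screening only

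*Protocol*

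**What the plan says.** Section 2.3.4.2 of the protocol summarises the clinical toxicology of intravenous ipilimumab. It names thyroid abnormalities among the inflammatory events of concern and says that clinical chemistries, "including liver function and thyroid function tests) should be evaluated at baseline and before each dose of Ipilimumab". Section 5.2 sets the local ipilimumab doses at "Week 12, 15, 18, and 21".

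Section 10 sets out the scheduled tests:

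- **Main calendar.** The row "Thyroid Stimulating Hormone" carries one mark, under screening. Its footnote 6 reads "Thyroid stimulating hormone with reflex T4" and gives no repeat timing. Footnote 2 fixes the screening window: "Screening assessments must be completed within 30 days of, and prior to the first dose of Nivolumab on Week 0 Day 1".
- **Repeated chemistry panel.** Footnote 4 lists "Glucose, urea nitrogen, creatinine, sodium, potassium, calcium, total and direct bilirubin, AST, ALT, alkaline phosphatase". Liver tests are included; TSH and T4 are not.
- **Vaccine/ipilimumab calendar.** Its safety-assessment row covers examination, vital signs, concomitant medications, "ECOG, CBC w/ diff, Serum Chemistry". There is no thyroid row.

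Section 5.3 asks for laboratory results to be reviewed before dosing but orders no thyroid test.

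**The concern.** One sentence recommends two kinds of test on the same occasions. The schedule implements the liver tests and omits the thyroid tests, and nothing in the protocol comments on the difference.

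The primary objective is safety. Sections 7.8.1.4 and 7.8.1.5 list endocrine toxicity as possible with both nivolumab and ipilimumab. Exclusion criterion 3.1.2.7 lets patients with autoimmune hypothyroidism on replacement enrol, so some may start with thyroid disease. Section 7.2.1 asks for laboratory abnormalities to be documented when they are clinically significant or need corrective treatment. An asymptomatic thyroid abnormality can meet that definition only if somebody measures it.

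Two things are at stake. The first is systematic detection of asymptomatic thyroid abnormalities during vaccine/ipilimumab dosing. The second is a reference value at week 12, after the nivolumab run-in. Without it, an abnormality found later cannot be dated to before or after the first vaccine/ipilimumab dose.

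**Working it through.** The plan states no figure on this point, so the check is a count and a date calculation.

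**Tests recommended and tests scheduled**

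- Recommended (Section 2.3.4.2 with the dosing in Section 5.2): 1 baseline + 4 pre-dose = 5.
- Scheduled (Section 10): 1, at screening.
- Difference: 5 − 1 = 4, which is all four pre-dose tests.

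If the week 12 value were itself taken as the ipilimumab baseline, the recommendation would come to four tests. None of those four would be scheduled.

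**Age of the screening TSH at each end of ipilimumab dosing**

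Screening falls 0 to 30 days before week 0, and 30/7 = 4.3 weeks.

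| Dose | Nominal week | Age of screening TSH (weeks) |
|---|---|---|
| First ipilimumab | 12 | 12 to 12 + 4.3 = 16.3 |
| Fourth ipilimumab | 21 | 21 to 21 + 4.3 = 25.3 |

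Nivolumab is given at weeks 0, 4 and 8 before the first ipilimumab dose. The week 12 nivolumab infusion follows ipilimumab on the day (Section 5.2.1.2). The only scheduled thyroid value therefore precedes three nivolumab doses. Section 5.2.1.2 also provides that if vaccine/ipilimumab therapy "gets delayed, vaccination timepoints will be modified as follows", so a late start makes the screening value older still.

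**How firm the screening-only reading is**

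The marks in these tables are not fully reliable as extracted. The main calendar shows a nivolumab mark at week 22, which does not fit four-weekly dosing, and the second calendar shows no administration mark under vaccine dose 2. A lost mark in the TSH row cannot be excluded. Three supports do not depend on mark positions: footnote 4 leaves TSH and T4 out of the panel, footnote 6 gives no repeat timing, and the second calendar has no thyroid row. Where other tests repeat, the footnotes say so: pregnancy tests every 4 weeks, and scans every 12 weeks after week 24.

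**Effect on the primary endpoint**

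Under Section 5.5 a DLT generally requires a grade 3 or 4 event or a treatment-related death. Grade 3 endocrine abnormalities corrected by hormone therapy within 4 weeks are excluded under the main toxicity criterion. An asymptomatic thyroid change would rarely count, so the DLT rate is little affected.

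**The case against.** The source sentence is background. It summarises experience with intravenous ipilimumab at 3 to 10 mg/kg and is worded as *should*. The same section puts exposure at the starting dose at about one thirtieth of the 3 mg/kg intravenous regimen, and Section 7.8.1.5 does not expect systemic reactions, though it allows for them. A lighter schedule could have been a deliberate choice. This stands to the extent that the mismatch is between a recommendation and a schedule; a reader might infer breach of a binding requirement, and the text does not support that. It does not remove the point, because Section 2.3.4.2 presents lower toxicity after local delivery as a hypothesis that this study examines.

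No readable section recommends periodic thyroid tests for nivolumab. That also stands. Nivolumab matters here because it is given before and during the dosing period, which is why a week 12 value would be useful.

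It is also fair to say that missed detection is inferred. Section 2.3.4.2 is itself protocol text that staff could have followed, testing at discretion is not barred, and the endocrine algorithm in Appendix B is a figure not available here. A reader might infer that thyroid events went unrecorded, or that thyroid counts from this trial carry no information. The documents show neither; both depend on what testing was done.

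**Conclusion.** The mismatch is real and modest. Of the five thyroid assessments that Section 2.3.4.2 implies, one is scheduled, and none falls within vaccine/ipilimumab dosing. If the calendars were followed, asymptomatic thyroid abnormalities were not systematically sought in that period, and no scheduled week 12 value exists.

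The conclusion assumes that the TSH row has no lost mark and that the calendars governed what was drawn. Ages of the screening value assume nominal dates.

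A reader might infer that the DLT rate or the MTD decision is compromised. Section 5.5 does not support that, and symptomatic events can still be found through examination and adverse event review at scheduled treatment visits. Nor would a week 12 TSH separate nivolumab from ipilimumab as the cause of a later event; it would only date the change. The documents give no thyroid event rate and no share of events detected without testing, so the number of events that might be missed cannot be estimated.

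**What to change.** For any patient still to be dosed, and for any reuse of the regimen, add TSH with reflex T4 before the ipilimumab doses at weeks 12, 15, 18 and 21, in both calendars and in footnote 6. Name week 12 as the pre-vaccine reference value. If vaccination is delayed, tie the tests to the actual doses.

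The cost is up to four assays per patient, on blood already drawn for CBC and chemistry at those visits. For two full cohorts of five that is at most 4 × 10 = 40 assays; the SAP does not state the number treated.

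The SAP (Modified Design) says that accrual stopped at the end of dose escalation, so the main remaining action is in reporting. The SAP's toxicity tables give worst grade per patient with no note on how events were sought. Report how many patients had on-treatment thyroid tests and when. If testing was not systematic, add one sentence saying that thyroid event counts reflect only clinically prompted detection.
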